METHODOLOGY: The specific aims are to: **(Aim 1)** Determine MR effectiveness for physical (pain, sleep), PTSD (intrusion, arousal, avoidance, numbing), and psychological (depression, stress, anxiety) symptoms, and global health (quality of life); **(Aim 2)** Determine MR effectiveness for social (relationship satisfaction, compassion for self/others) outcomes among Veterans and their partners; and **(Aim 3)** Describe Veteran and partner perceived value of MR in a sub-sample of participants. The sample will consist of Veteran and partner dyads (N = 600). **Aim 1 & 2** data collection will include self-report assessment of 4-data points over a 4-month period to evaluate physical, psychological, and social outcomes. Eight weekly reports will also be collected for the first two months of MR use to assess MR utilization, and pain and stress levels. **Aim 3** data collection will include telephone interviews from a selected sub-sample of 84 individuals to examine MR user experiences, study experiences, and to collect their suggestions for making MR useful for Veterans and their partners.

CLINICAL RELEVANCE: In a community-based trial in a non-clinically defined sample of Veterans, MR was associated with significant reductions in pain and PTSD-related symptoms. In the proposed study we will test MR's effects in a clinically defined population as a complement to clinical services. This program evaluation is needed to determine MR's appropriateness for implementation within the VA for clinically defined populations.

Aim 1: Determine MR effectiveness for physical (pain, sleep), PTSD (intrusion, arousal, avoidance, numbing), and psychological symptoms (depression, stress, anxiety), and global health (quality of life).

H1.1. Veterans who use MR will report significantly greater improvement in physical pain compared to those in the control group. (Primary Outcome)

H1.2. Veterans who use MR will report significantly greater improvement in PTSD and psychological symptoms, sleep and quality of life compared to those in the control group. (Secondary Outcomes)

Aim 2: Determine MR effectiveness for social (relationship satisfaction, compassion for self/others) outcomes among Veterans and their partners.

H2.1. Veterans and partners who use MR will report significantly greater improvement in social outcomes compared to the control group. (Secondary Outcomes)

Aim 3: Describe Veteran and partner perceived value of MR in a sub-sample of participants.

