Aim 1 & 2 assessment data will be collected from 600 Veteran/partner dyads (up to 200 per site, 100 dyads per arm) via a secure project website at baseline, 1, 2, and 4 months to assess primary and secondary outcomes. MR utilization and pain ratings will be assessed weekly for the first eight weeks of the intervention. This data collection plan will allow assessment of acute changes, rate of change with repeated measures over two months and sustained changes.

In **Aim 3**, a sub-sample of 84 individuals assigned to the intervention arm (n= 84 individuals, approximately 28 individuals/site) will be purposively selected (e.g., high or low MR utilization groups) to participate in telephone interviews to evaluate their experiences using the program. All consenting participants will be randomly assigned in a 1:1 ratio *using a permuted variable block design* to one of two arms (treatment vs. control). Participants will receive study information, instructions on how to complete the online data collection, and contact information in case they experience an adverse event. Participants will provide preferred contact information for data collection reminders. We will have contact information for each participant's primary care provider to ensure contact in the case of an adverse event and follow our established protocol for such events.

Treatment Arm: MR is a user-driven, dyadic, self-care management program developed with NIMH funding (R43/44) for use by Veterans and their selected partners, individually or together, to reduce pain and distress and support physical, mental, and relationship health. MR was designed for Veterans who face obstacles accessing formal mental health services. It can also be used to complement formal services. MR is a patient-centered intervention, allowing users to determine the pace at which to proceed in each program component.

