Sampling: We will use a four-step process to purposively recruit study participants (see Figure 2). First, using an IRB approved procedure with a waiver of consent process; a secondary administrative data query of the ICD-9-10 conditions for chronic pain and PTSD will identify a sample pool of Veterans in the previous fiscal year. Cross-examination of the pain and PTSD cohorts for FY 2016 indicates a sample of 5,508 in Tampa who will be potential participants [Source: VSSC, Diagnosis Pyramid Analytics Report: Accessed 08/27/2017]. With our access levels and expertise, this process should take two weeks. Second, we will recruit from providers using signed letters from the PI. The provider will give the recruitment letter to the patient for him/her to follow up with the study team member to inquire about participating in the study. Study team members will mail the same recruitment letters to cohorts who have been identified in step one of the recruitment process to reduce burden of clinical partners and to reach those Veterans who don't often attend VA medical appointments. This helps provide a way to reach out to those Veterans with this type of diagnoses who are less likely or don't regularly receive care intervention. Potential participants who contact study staff after receiving a recruitment letter will be presented with information about the study to help them determine whether they'd like to participate in the study and provide a verbal consent and HIPPA authorization. Potential participants who have not responded to the letter may be contacted by their healthcare team for follow-up. Based on our previous projects the process from initial sampling to recruitment and randomization should conservatively take three months.

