Sample Size Power Analysis: Aim 1&2, H1.1-H1.2 & H2.1 estimates of statistical power are based on Aim 1 and initially the primary outcome of pain. Whereas dyad is the unit of randomization, we assess power based on separate analyses for Veterans and partners (one approach used). There are 4 major intervals of assessment (baseline, 1, 2, and 4-months). At the beginning of this study, we estimated attrition based off of a previous MR trial that had less than 5% attrition. Based on early recruitment at the primary site, we have adjusted recruitment goals to allow for approximately 33% attrition, and uneven recruitment across the three study sites. Assuming within-subject (outcome measurement) correlation of 0.5, the proposed sample size will provide 80% power (2-sided type I error rate of 0.05) to detect a “small-to-medium” effect size of 0.38 (Cohen’s d). For analyses stratified by site (in addition to evaluation by random effect assessment), the study will provide 80% power to detect a “medium-to-large” effect size of 0.66. By way of comparison, the pilot data presented above describes large effect sizes ($d = 0.81$ for pain symptom reduction). While this effect size was based on a relatively small sample of comparable patients ($n < 15$) and within-subject assessment (paired t -test), it provides good assurance that the proposed sample size is sufficient to detect realistic, medium size effects should they exist with the MR program. For secondary outcomes, we will use a type I error rate of 0.01 for multiple comparisons. For the sample and our described assumptions, this will provide 80% power to detect a “medium” effect size of 0.45.⁵⁹

Sample Size: Qualitative- Aim 3 sample size relies on the quality and richness of information obtained.⁶⁰ Conceptual saturation is the goal of qualitative research, and depends on data to support interpretations. Saturation has been noted to occur within the first 12 interviews.^{60,61} Our team has extensive experience in evaluating electronic technologies, and have found recruiting high and low volume users provides the richest dataset. To ensure representative data, we will conduct telephone interviews with a purposive (e.g., high or low MR utilization group) sub-sample of up to 84 individuals to achieve representation at each site (approximately 28 individuals/site).

Data Collection Procedures. Data will be collected using (1) self-report surveys; and (2) telephone interviews.

(1) Self-reported Survey Data.

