Marketing Materials	Veterans and family members, Veteran Service Organizations, VEC	• Increased motivation to actively use MR for non-pharmacological self-care management
4. System-wide presentation of in-service and marketing of implementation strategies		
TMS/EES Presentation	VHA Employees VISN PACT Leads & Virtual Care Coordinators	• Present findings and increase awareness of MR • Lessons learned, recommendations, and MR use strategies
5. Cyber Seminar		
Oral Presentation	VA Researchers & Administrators	• Present findings and increase awareness of MR • Lessons learned and MR use strategies

Project Management Plan

This team has established effective mechanisms for communication and collaboration leveraging technology across sites. The Tampa based team, led by [name], will direct overall coordination of the project. [name] will work with co-investigators to refine and implement data collection and analyses, and ensure the project is achieving study benchmarks. [name] will lead randomization and quantitative data analyses for **Aims 1 & 2**. PI and study team will lead qualitative activities for Aim 3. Drs. [name], [name], and [name] will provide clinical expertise and recruitment support at the Tampa site.

Table 3. GANTT Chart of Study Benchmarks.

Project activity	YEAR 1 (2019-2020)				YEAR 2 (2020-2021)				YEAR 3 (2021-2022)				YEAR 4 (2022-2023)			
	Q1 Nov '18	Q2 Feb '19	Q3 May	Q4 Aug	Q1 Nov	Q2 Feb '20	Q3 May	Q4 Aug	Q1 Nov	Q2 Feb '21	Q3 May	Q4 Aug	Q1 Nov	Q2 Feb '22	Q3 May	Q4 Aug
Start-up																
Recruitment Screening and Randomization, Qualtrics development and validation																
Recruitment (3-4 dyads/month per site)																
Primary Data Collection																
Conduct Interviews																
Interview Transcription																
Interview Data Analysis																
Prepare & Stage Primary Data																
Primary Data Analysis																
Data Interpretation and Triangulation																
Finalize Data Reports/Manuscripts																
Develop Materials for Dissemination																
Prepare/Submit Subsequent Proposal																
Disseminate Materials to Audiences																

Resources and Specific Location of Study

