(3) Polytrauma Rehabilitation Center, Tampa, FL. Under the leadership of [name] (research team Co-Investigator), Tampa has the largest of five designated Polytrauma Rehabilitation Centers in the VHA. The program includes a Polytrauma Network Service, a mild TBI program, a Disorders of Consciousness Program, and a 10-bed transitional living unit. The Tampa VA is one of four VAMCs in the collaborative Defense and Veterans Brain Injury Center (DVBIC), designed to ensure that all military and Veterans receive TBI specific evaluation, treatment, and follow-up, while collecting standardized patient outcome data to compare the relative efficacy of various treatment and rehabilitation strategies. Tampa also participates in the VA/TBI Model Systems collaborative and collects comparable data on Veterans. Researchers at the Tampa R&DS and the clinical staff at the Tampa Polytrauma Rehabilitation Centers (PRCs) have a 10-year history of strong collaboration as evidenced by joint publications and co-investigator status on HSR&D and RR&D-funded studies. Polytrauma Rehabilitation System of Care provides specialized rehabilitation for Veterans and Service Members with polytrauma and TBI to restore multiple skills and facilitates the transfer of those skills from the hospital setting to daily life. VA's PRCs provide the most intensive, specialized and comprehensive rehabilitation care for Veterans and Service members with complex and severe polytrauma. Polytrauma injuries involve more than one physical region or organ system, one of which may be life threatening, and which results in physical, cognitive, psychological, or psychosocial impairments and functional disability. The PRCs embrace an interdisciplinary team approach to plan and administer an individually tailored rehabilitation plan to help the patient recover to the fullest extent possible. Each PRC is accredited by the Commission on Accreditation of Rehabilitation Facilities and serves as a resource to develop educational programs and best practice models for other facilities across the system.

Probable Duration of the Project

The projected study period to complete this research is four years. The anticipated start date will occur by November 1, 2018. The PI and study team will conduct a continuing review for approval annually and comply with required reporting based on risk associated with the study. See Table 3 for the GANTT study timeline.

Privacy and Information Security Information

1. Risk to Subjects

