A) Human Subjects Involvement and Characteristics

In Aims 1-2 we estimate a recruitment sample size of 600 dyads, with approximately 33% over-sampling for attrition. We will recruit a sample of up to 200 Veteran/partner dyads (total 600 dyads) at each of the three sites to allow even numbers of dyads to be assigned to treatment and control arms. We will use a four-step process to purposively recruit study participants (see Figure 2). First, using a standard IRB approved procedure with a waiver of consent; a secondary administrative data query of the ICD9/10 conditions for chronic pain and PTSD will identify a sample pool of Veterans in the previous fiscal year. Cross-examination of the pain and PTSD cohorts for FY 2015 indicate a sample of 5,508 in Tampa who will be potential participants [Source: VSSC, Diagnosis Pyramid Analytics Report: Accessed 04/27/2017]. With our access levels and expertise, this process should take two weeks. Second, we will recruit from providers using signed letters from the PI. The provider will give the recruitment letter to the patient for him/her to follow up with the study team member to inquire about participating in the study. Study team members will mail the same recruitment letters to cohorts who have been identified in step one of the recruitment process to reduce burden of clinical partners and to reach those Veterans who don't often attend VA medical appointments. This helps provide an effective way to reach out to those Veterans with this type of diagnoses who are less likely or don't regularly receive care intervention. Potential participants who contact study staff after receiving a recruitment letter will be presented with information about the study to help them determine whether they'd like to participate in the study and provide a verbal consent and HIPPA authorization. Potential participants who have not responded to the letter may be contacted by their healthcare team for a follow-up. This procedure has been approved in other studies and provides an effective way to reach out to those Veterans with this type of diagnoses who are less likely or don't regularly receive care intervention. Based on our previous projects the process from initial sampling to recruitment and randomization should conservatively take three months.

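### At 3-4 dyads per month per site, three sites cannot recruit 600 dyads in four years, and the stated detectable effects fit about 218-232 analysed dyads, not 600 less 33%

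*Combined protocol and SAP*

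**What the plan says.** The target is 600 dyads throughout. The summary under Methodology says "The sample will consist of Veteran and partner dyads (N = 600". Study Design and Overview repeats it as "600 Veteran/partner dyads (up to 200 per site, 100 dyads per arm". Human Subjects Involvement and Characteristics says "We will recruit a sample of up to 200 Veteran/partner dyads (total 600 dyads) at each of the three sites". The Sample section gives 200 dyads for Tampa, which agrees with 200 per site.

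The only accrual rate is in Table 3 (GANTT chart): "Recruitment (3-4 dyads/month per site". Probable Duration of the Project says "The projected study period to complete this research is four years". The Sampling section adds that "the process from initial sampling to recruitment and randomization should conservatively take three months", and each dyad is followed for four months.

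Sample Size Power Analysis says that recruitment goals were adjusted "to allow for approximately 33% attrition" and for uneven recruitment across sites. It then claims 80% power, two-sided, for d = 0.38 overall at alpha 0.05, d = 0.66 within a site, and d = 0.45 for secondary outcomes at alpha 0.01. It assumes a within-subject correlation of 0.5 and analyses Veterans and partners separately. Human Subjects Involvement and Characteristics describes the same 600 as "with approximately 33% over-sampling for attrition". Neither the protocol nor the Updated Statistical Analysis Plan states an analysed N, or the N behind the three effect sizes.

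**The concern.** Target, accrual rate, duration, attrition and detectable effects should form one chain: rate times window gives the number recruited, attrition gives the number analysed, and that number gives the detectable effects. Here the chain breaks in two places. The rate does not reach the target inside the project, and the detectable effects are not those of the target after attrition.

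These are the figures against which recruitment will be monitored and a null result interpreted. A reader who takes d = 0.38 as the limit of what the trial can detect would be using a figure that belongs to a much smaller analysed sample than 600 recruits imply. A reader who takes 600 as the expected size would be relying on a number that the plan's own accrual does not produce.

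**Working it through.** **Inputs.** 3-4 dyads/month per site (Table 3); 3 sites and 600 dyads (Human Subjects Involvement and Characteristics); 48 months (Probable Duration of the Project); 3-month lead-in (Sampling); 4-month follow-up (Methodology); 33% attrition, 80% power, and alpha 0.05 or 0.01 two-sided (Sample Size Power Analysis); 1:1 allocation (Study Design and Overview).

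**Accrual.**
- Monthly total: 3 × 3 = 9 to 3 × 4 = 12 dyads.
- Time for 600: 600/12 = 50.0 months to 600/9 = 66.7 months, against 48.
- All 48 months used: 48 × 9 = 432 to 48 × 12 = 576.
- Assumed 41-month window (48 − 3 − 4): 41 × 9 = 369 to 41 × 12 = 492.
- Rate per site that 600 needs: 200/48 = 4.17 a month, or 200/41 = 4.88 a month.

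**The plan's own detectable effects.** For a two-sample comparison with SD 1, n per arm = 2(z₁₋α/₂ + z₀.₈₀)²/d². The sum of the z-values is 1.960 + 0.842 = 2.802 at alpha 0.05, and 2.576 + 0.842 = 3.418 at alpha 0.01.

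| Stated effect | n per arm | Total dyads |
|---|---|---|
| d = 0.38, alpha 0.05 | 2 × 2.802²/0.38² → 109 | 2 × 109 = 218 |
| d = 0.66 within site, alpha 0.05 | 2 × 2.802²/0.66² → 37 per arm per site | 6 × 37 = 222 |
| d = 0.45, alpha 0.01 | 2 × 3.418²/0.45² → 116 | 2 × 116 = 232 |

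The three stated effects agree with one another at about 218-232 analysed dyads. They do not reproduce 600 or 600 × 0.67 = 402.

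**What 402 would detect.** With 201 per arm (67 per arm per site), d = (sum of z) × √(2/n):
- overall: 2.802 × √(2/201) = 0.28
- within site: 2.802 × √(2/67) = 0.48
- alpha 0.01: 3.418 × √(2/201) = 0.34

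Equivalently, 402 analysed gives power of 96.8%, 96.9% and 97.4% for the three stated effects, not 80%.

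**Does the 0.5 correlation explain the gap?** No. A change-score analysis has variance factor 2(1 − 0.5) = 1, so it returns the same 218, 222 and 232. Baseline-adjusted ANCOVA (factor 1 − 0.25 = 0.75) needs 164-174. Averaging three or four measurements, with or without baseline adjustment, needs 92-154. Each of these moves further from 402.

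**Power at the accrual-limited size.** After 33% loss, 48 months leaves 432 × 0.67 = 289 to 576 × 0.67 = 386 dyads, with 90-96% power for d = 0.38. The 41-month window leaves 369 × 0.67 = 247 to 492 × 0.67 = 330, with 85-93%.

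**Recruits that the stated effects need.** 218/0.67 = 326 to 232/0.67 = 347. At 9-12 a month that is 326/12 = 27 to 347/9 = 39 months. The accrual rate and the power paragraph are therefore compatible with each other, and 600 is the figure that does not fit.

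**The case against.** Two of the per-site statements give 200 as an upper limit, the power paragraph allows for uneven sites, and the bars of the GANTT chart cannot be read. This does not rescue the plan. The Methodology summary gives 600 without qualification, Human Subjects Involvement and Characteristics calls it the estimated recruitment sample size, and no window inside 48 months reaches it at the stated rate.

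The effect sizes computed here treat the analysed set as completers in a two-sample comparison. The plan uses intention to treat, mixed models over four time points and additional multiple-imputation analyses, so partial responders can contribute. That stands: 0.28, 0.48 and 0.34 are simplified values. It does not close the gap, because using more of the data makes the effects detectable with 600 recruits smaller still.

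A reader might infer that the analysable N is misstated. The documents do not support that, because they state none. Attrition of 33% leaves 402. Over-sampling of 33% on a base would imply 600/1.33 = 451, which covers only 24.8% loss. But the second wording may be a loose description of the same allowance, so this is an ambiguity to clear up and not a demonstrated error.

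A reader might also subtract only the last follow-up and adopt 44 × 9 = 396 to 44 × 12 = 528 as a new target. That ignores start-up, the three-month lead-in and analysis time. With the window unreadable, no specific replacement N can be supported.

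**Conclusion.** The concern holds as an inconsistency among stated figures. At the stated rate the most that four years can yield is 576 dyads, and about 369-492 under an assumed 41-month window that still leaves no time for analysis. The stated detectable effects belong to about 218-232 analysed dyads, a little over half of the 402 that 600 recruits with 33% attrition would leave.

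It is tempting to conclude that the trial is underpowered. The documents do not support this for d = 0.38: power is about 85-96% across the 41- and 48-month windows. That statement depends on the unreadable recruitment window. At 36 months and 3 per site per month, 324 × 0.67 = 217 would remain, which is about break-even with the 218 needed.

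The accrual result rests only on the plan's own rate, number of sites and duration. The effect-size result also assumes a simple two-sample comparison with 33% lost from those randomised.

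**What to change.** 1. State the recruitment window in months and reconcile Table 3 with the target. Give either the N that 3-4 dyads per site per month delivers in that window, or the rate that 600 requires: at least 4.2 per site per month if all 48 months were used, about 4.9 over 41 months, and more if analysis time is set aside.
2. Define the 33% once, as loss from those randomised, so that recruited N = analysed N/0.67. Use that definition in both Sample Size Power Analysis and Human Subjects Involvement and Characteristics.
3. State the resulting analysed N and recompute the three detectable effects (overall, within site, and at alpha 0.01) from it. Show the method and how the 0.5 correlation enters.

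The cost is protocol wording and a short recalculation. It needs no extra participants and no change to the analysis.
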